8. STUDY PROCEDURES

Not applicable.

9. SAFETY

Regarding management and reporting of adverse events/adverse reactions:

This study is an observational, retrospective, post-authorization safety study, based on data extracted from KPSC databases. Safety as an endpoint will be reported in aggregate; individual case adverse event/adverse reaction reports will not be generated from this study.

Spontaneous reports of serious adverse events (SAEs) received by GSK are processed according to standard pharmacovigilance procedures, which include reporting of adverse events, adverse reactions, and SAEs, to regulatory authorities.

10. DISCONTINUATION/WITHDRAWAL CRITERIA

Not applicable.

11. STATISTICAL CONSIDERATIONS

11.1. Sample size determination and power estimation

[Table 5](#) describes the expected number of individuals ages ≥ 18 years at KPSC that will be available for full analyses for VE and safety objectives.

[Appendix 4](#): Sample size for early analyses of primary objectives among individuals ≥ 50 years of age shows similar tables with expected sample size and timelines for early analyses in individuals ages ≥ 50 years.

Table 5 Sample size and average follow-up time per person (ages ≥18 years) for full analyses

	Sample size for eligible 2-dose RZV recipients ¹ (regardless of RA or IBD)	Average follow-up time (years) by 8/2024	RA cohort ²	IBD cohort ³
2018	12100	5.8	118	96
2019	53400	5.1	505	386
1/2020-2/2020 ⁴	12000	4.5	112	58
2021 (estimate)	40000	3.1	364	220
2022 (estimate) ⁵	40000	2.1	444	373
1/2023-8/2023 (estimate)	27000	1.2	300	252
Average follow-up time (weighted)		3.5		
Total sample size of 2-dose RZV recipients			1843	1385
Total sample size of at least 1-dose RZV recipients			3071	2308

ACIP = Advisory Committee on Immunization Practices; COVID-19 = Coronavirus Virus Disease 2019; IBD = Inflammatory bowel disease; KPSC = Kaiser Permanente Southern California; RA = rheumatoid arthritis; RZV = Recombinant zoster vaccine; ZVL = Zoster vaccine live

¹Based on May 2020 uptake and historical ZVL uptake, accounting for 1-year membership prior to index date.

²Based on May 2020 uptake, 0.91% of vaccinees age 50+ are RA patients (2 diagnosis codes in year prior to index), and 18% RA patients are age 18-49, accounting for 1-year membership prior to index date.

³Based on May 2020 uptake, 0.55% of vaccinees age 50+ are IBD patients (2 diagnosis codes in year prior to index), and 41% IBD patients are age 18-49, accounting for 1-year membership prior to index date.

⁴Vaccine accrual period in 2020 shortened due to impact of COVID-19 on vaccination and health care-seeking behaviors.

⁵Assuming ACIP recommendation of 18+ for immunocompromised individuals in Oct 2021, with KPSC use beginning Jan 2022.

11.1.1. VE

The sample size calculation for the primary VE objectives was conducted using a two-sided log rank test with alpha=0.05, to achieve 80% statistical power, assuming a range of HZ incidence rates in the RZV unvaccinated group (12, 15, 18, 20 per 1000 person-years) [Yun, 2016], a detectable HR of 0.1 to 0.4 (VE of 60% to 90%), a ratio of RZV vaccinated to RZV unvaccinated of 1:3, and a censoring rate of 7% in the RZV vaccinated group (due to termination of membership, or death) and 25% in the RZV unvaccinated group (due to termination of membership, death, or receipt of zoster vaccine). The calculation was performed using SAS software package (version 9.3) PROC POWER procedure.

Table 6 shows that in a cohort study with 1:3 matching ratio and an average 3.5 years of follow-up, the number of vaccinated subjects needed to detect a VE of 60, 70, 80, 90% with 80% power and a type 1 error rate of 5% is 564, 397, 291, and 219, respectively, assuming the incidence of HZ in the unvaccinated population is 15/1000 person-years.

The expected number of RA and IBD patients who will receive 2 doses of RZV (4 weeks to 6 months apart) during the assumed accrual period between 5/2018 to 8/2023 is 1843 and 1385 (Table 5), respectively, substantially exceeding the required numbers illustrated in Table 6. This demonstrates that the study is sufficiently powered to assess the primary VE objectives.

The power for analyses of secondary or exploratory objectives could vary and may not reach 80% depending on available sample size.

Table 6 VE sample size required for individuals ages ≥18 years to achieve 80% power, given alpha=0.05, and different detectable HR (or VE)

Average length of follow-up (years)	Incidence rate in RZV unvaccinated group (cases/1000 person-years) ¹	HR	VE (%)	Total sample size	Sample size of RZV vaccinated group ²
3.5	12	0.1	90	1096	274
		0.2	80	1452	363
		0.3	70	1984	496
		0.4	60	2816	704
	15	0.1	90	876	219
		0.2	80	1164	291
		0.3	70	1588	397
		0.4	60	2256	564
	18	0.1	90	732	183
		0.2	80	968	242
		0.3	70	1324	331
		0.4	60	1880	470
	20	0.1	90	656	164
		0.2	80	872	218
		0.3	70	1192	298
		0.4	60	1696	424

HR = Hazard ratio; VE = Vaccine effectiveness; RZV = Recombinant zoster vaccine; % = Percentage

¹[Yun, 2016]

²The number can be compared with the numbers in Table 5, demonstrating that the study is powered to assess the primary VE objectives.

11.1.2. Safety

The power calculation for the SCCS design is based on the signed root likelihood ratio method [Musonda, 2006]. Let k be the ratio of the length of comparison window vs. length of risk window. The number of flares that need to be observed in the risk window and comparison window to achieve 80% power is shown in Table 7 for different values of detectable RR.

Vaccination (first dose)*: Day 0

Risk period: +1 to +30 days

Comparison period: (-90 to -61 days) AND (+31 to +60 days)

Washout period: -60 to -1 days

**The current sample size calculations are based on the first RZV dose only. The design can be extended to include second RZV dose exposure. The total length of the risk windows and comparison windows will depend on the timing of receipt of the second dose.*

Table 7 Sample size required for individuals ages ≥18 years to achieve 80% power, given alpha=0.05, k=2 and different detectable RR for safety

k	RR	No. of events in the risk period	No. of events in the comparison period
2	1.2	386	643
2	1.5	87	115
2	2	34	34
2	3	16	10

No = Number; RR = Relative risk

Our SCCS design requires at least 115 events in the comparison window to achieve 80% power of detecting an increased risk of flare of RR=1.5 with a type 1 error rate of 5%.

Table 8 Estimated flares and detectable RR for safety among RA cohort ages ≥18 years who receive at least one dose of RZV

Sample size of RA cohort ¹	RA flare rate (per 30 days) ²	Number of flares in comparison window (60 days)	Detectable RR ³
3071	1.5%	92	2
3071	2.5%	154	1.5
3071	3%	184	1.5
3071	3.5%	215	1.5
3071	5%	307	1.5
3071	7%	430	1.5

RA = Rheumatoid arthritis; RR = Relative risk; RZV = Recombinant zoster vaccine

¹Sample size from [Table 5](#) (total sample size of at least 1-dose recipients).

²[[Bechman, 2018](#) ; [Bykerk, 2014](#) ; [Markusse, 2015](#); [Stevens, 2020](#)].

³Compare with [Table 7](#).

With 3071 RA patients expected to receive at least one dose of RZV during the accrual period ([Table 5](#)), there will be 154 flares in the 60 days comparison period, assuming the flare rate in RA patients is 2.5% in 30 days. This would allow us to detect an increased risk of flare of RR=1.5 (risk of flare in the risk window vs. risk of flare in the comparison window) with 80% power and 5% type 1 error rate ([Table 8](#)).

With 2308 IBD patients expected to receive at least one dose of RZV during the accrual period (Table 5), there will be 138 flares in the 60 days comparison period, assuming the flare rate in IBD patients is 3% in 30 days. This would allow us to detect an increased risk of flare of RR=1.5 (risk of flare in the risk window vs. risk of flare in the comparison window) with 80% power and 5% type 1 error rate (Table 9). The power for analysis of the secondary objective may not reach 80% if the number of events is less than the desired size due to smaller sample size in IBD subgroups.

Table 9 Estimated flares and detectable RR for safety among IBD cohort ages ≥18 years who receive at least one dose of RZV

Sample size of IBD cohort ¹	IBD flare rate (per 30 days) ²	Number of flares in comparison window (60 days)	Detectable RR ³
2308	1%	46	2
2308	1.5%	69	2
2308	2%	92	2
2308	3%	138	1.5
2308	4%	185	1.5

IBD = Inflammatory bowel disease; RR = Relative risk; RZV = Recombinant zoster vaccine

¹Sample size from Table 5 (total sample size of at least 1-dose recipients).

²[Bolge, 2010 ; Satyam, 2020 ; Rahier, 2011].

³Compare with Table 7

11.2. Statistical analyses

11.2.1. Descriptive

For the VE analyses, the number and characteristics of individuals in each cohort will be described and compared. Categorical variables such as those listed above will be presented as absolute numbers and percentages with p-values for the Pearson χ^2 test or Fisher's exact test, as appropriate. Continuous variables such as age in years will be presented as the mean with standard deviation and/or median with interquartile ranges, with p-values for the two-sample t-test or Wilcoxon rank-sum test, as appropriate. Absolute standardized differences will be calculated to assess the balance of covariates. Overall incidence rates of HZ for the 2-dose (4 weeks to 6 months) RZV vaccinated cohort and the matched unvaccinated cohort will be calculated by dividing the number of HZ cases by the total number of person-years.

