7.4. Matching for VE analyses

For secondary VE objectives 1-3, secondary VE objective 5, and exploratory VE objectives 1-4, individuals meeting inclusion criteria who receive 2 doses of RZV at least 4 weeks apart through the end of the accrual period will be matched with unvaccinated individuals who have not received any doses of RZV as of the index date at a ratio of 1 to up to 3. For secondary VE objective 4, individuals meeting inclusion criteria who receive 2 doses of RZV >6 months apart through the end of the accrual period, and for primary VE objectives 1-2, individuals meeting inclusion criteria who receive 2 doses of RZV 4 weeks to 6 months apart, and their respective matched unvaccinated comparators will be included. No separate matching is needed.

Matching variables will comprise the following:

- Condition (RA, UC, CD)
- Age (by decade) at index date
- Sex
- Race/ethnicity, if sample size allows
- Medication category at index date (detailed in [Appendix 3](#)).

For secondary VE objectives 6-7, individuals who receive 1 dose of RZV but do not receive a second dose 4 weeks to 6 months after the first dose will be matched with unvaccinated individuals who have not received any doses of RZV as of the index date at a ratio of 1 to up to 3. The 1-dose person-time will be censored upon receipt of the second RZV dose received >6 months after the first dose. Matching variables will comprise condition (RA, UC, CD), age (by decade) at index date, sex, race/ethnicity (if sample size allows), and medication category at index date.

The 2-dose (4 weeks to 6 months) RZV cohort and 1-dose RZV cohort will be mutually exclusive. Unvaccinated individuals who are matched to RZV vaccinated individuals can contribute person-time to a vaccinated cohort if they receive RZV; their unvaccinated person-time is censored upon receipt of the first dose of RZV.

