11.2.2. Primary analyses

For primary VE objectives 1-2, the number of incident HZ cases and the number of person-years of follow-up for subjects will be assessed for the 2-dose (4 weeks to 6 months) RZV cohort and the matched unvaccinated cohort.

Unadjusted and adjusted HRs and 95% confidence intervals (CIs) comparing HZ incidence rates in the 2-dose (4 weeks to 6 months) RZV cohort and the matched

unvaccinated cohort will be estimated by Cox stratified proportional hazards regression models without and with adjusting for potential confounders described above. Estimates of VE (%) will be calculated as $(1 - \text{HR}) \times 100$ when the HR is less than or equal to 1, and $([1/\text{HR}] - 1) \times 100$ when the hazard ratio is greater than 1.

The VE of 2 doses of RZV by time since vaccination will also be evaluated.

For the primary safety analyses, characteristics of individuals with RA or IBD who meet inclusion criteria will be described. Incidence rates for RA or IBD (UC or CD) flare for risk periods and comparison periods will be calculated by dividing the number of flares by person-time. Relative risks (95% CI) for flare comparing risk and comparison periods overall and by first dose and second dose will be estimated using conditional Poisson regression.

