11.2.4. Exploratory analyses

Exploratory VE objectives 1-2: Analyses for exploratory VE objectives 1-2 (2 doses of RZV given at least 4 weeks apart) will employ similar methods as for the primary VE objectives. In exploratory VE objective 1, analyses for RA (primary VE objective 1) will be stratified by medication category at index date ([Appendix 3](#)). In exploratory VE objective 2, analyses for IBD (primary VE objective 2) will be stratified by medication category at index date ([Appendix 3](#)). Descriptive analyses and multivariable Cox proportional hazards regression will be conducted by strata and estimates of VE (%) will be calculated as $(1 - \text{adjusted HR}) \times 100$.

Exploratory VE objectives 3-4: For exploratory VE objectives 3-4, the incidence of PHN, disseminated HZ, HZ-related meningoencephalitis, and hospitalized HZ will be described in 2-dose (2 doses of RZV given at least 4 weeks apart) RZV vaccinated and unvaccinated adults ≥ 18 years with RA (exploratory VE objective 3) and IBD (exploratory VE objective 4). The proportion of HZ cases with PHN, disseminated VZV, VZV-related meningoencephalitis, and hospitalized HZ will also be described among RZV vaccinated and unvaccinated adults ≥ 18 years with RA and IBD. Hospitalized HZ will be evaluated in the final analysis only (i.e., not in the interim analysis).

Exploratory safety objectives 1-2: In exploratory safety objective 1, analyses for RA (primary safety objective 1) will be stratified by medication category at index date ([Appendix 3](#)) if sample size allows. In exploratory safety objective 2, analyses for IBD (primary safety objective 2) will be stratified by medication category at index date ([Appendix 3](#)) if sample size allows.

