13.3. Appendix 3: Medication categories

- a. Vaccinated and unvaccinated subjects will be matched on age, sex, race/ethnicity (if sample size allows), autoimmune disease (RA, CD, UC), and medication category (as a proxy for disease severity and risk of HZ) at the beginning of follow-up (index date). The medication categories were developed based on consultation with KPSC and external experts (rheumatologists and gastroenterologists) to ensure matching based on differences in disease severity and risk of HZ.
- b. Search period
 - Rituximab (Rituxan) or rituximab-abbs/rituximab-pvvr (Truxima): 6 months before index date¹
 - Biologics: 3 months before index date²
 - JAK inhibitors, sphingosine-1 phosphate (S1P) receptor modulators, cyclosporine: 3 months before index date to 1 month after index date³
 - Nonsteroidal anti-inflammatory drugs (NSAIDs), 5-aminosalicylate (5-ASA), aminosalicylate, sulfasalazine, thiopurines, steroids, and conventional DMARDs: Medication prescribed/refilled within 6 months prior to index date AND medication duration covers the index date⁴
- c. Medication category will be determined by the highest category of medication during the search period.
- d. Medication categories may be consolidated to ensure at least 1:1 matching.

¹Rituximab is typically dosed every 6 months, so the search period for rituximab is 6 months before the index date.

²Some biologics are given as far apart as every ~8 weeks, so the search period for biologics is 3 months before the index date.

³The search period for JAK inhibitors and S1P modulators is extended to 1 month after the index date; because JAK inhibitors and S1P modulators are associated with a significantly increased risk of HZ, [Bechman, 2019; Choden, 2022; Colombel, 2018; Curtis, 2019; Lasa, 2021; Marra, 2016; Sandborn, 2019; Winthrop, 2017; Yun, 2015] providers may administer RZV prior to initiating treatment with a JAK inhibitor or S1P modulator. Since cyclosporine is included in the same IBD medication category as JAK inhibitors and S1P modulators, the same search period will be used.

⁴While medications are typically dispensed as a ≤ 90 -day supply, some medications are occasionally dispensed as a ≥ 100 -day supply. To ensure identification of prescriptions covering the index date, medications prescribed/refilled within 6 months prior to the index date will be searched to identify those medications with a duration covering the index date.

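### With 1 to up to 3 matching, the pooled unvaccinated HZ rate may not carry the vaccinated cohort's risk mix; weight descriptive comparator figures by set size

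*Protocol*

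**What the plan says.** Section 7.4 matches two-dose recipients to people "who have not received any doses of RZV as of the index date at a ratio of 1 to up to 3", on condition, age decade, sex, medication category and, if numbers allow, race/ethnicity. Appendix 3 (section 13.3) sets the floor: "Medication categories may be consolidated to ensure at least 1:1 matching". So set size is allowed to vary from one to three.

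Section 11.2.1 states that overall HZ rates in the primary two-dose cohort and its matched unvaccinated cohort "will be calculated by dividing the number of HZ cases by the total number of person-years". No weighting or standardisation is mentioned. The same section says "Absolute standardized differences will be calculated to assess the balance of covariates", without saying how.

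Table 1 in section 4 lists the HZ incidence rate as an outcome of both primary VE objectives. VE itself is taken from hazard ratios: section 11.2.2 says that HRs for the vaccinated against the matched "unvaccinated cohort will be estimated by Cox stratified proportional hazards regression models without and with adjusting for potential confounders described above". For exploratory VE objectives 3-4, section 11.2.4 says only that the incidence of PHN, disseminated HZ, "HZ-related meningoencephalitis, and hospitalized HZ will be described in 2-dose" vaccinated and in unvaccinated adults, and that the proportions among HZ cases will be described too. No hazard ratio is specified for these outcomes.

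**The concern.** When every set has the same number of comparators, the pooled comparator group has the vaccinees' distribution of the matching variables at the index date. When the number varies, a set with three comparators counts three times as much in the pooled rate as a set with one. The pooled group then leans towards the cells where comparators are plentiful.

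That matters only if set size is related to HZ risk. The protocol gives reason to think that it could be. Section 3 names increasing age and immunosuppression as risk factors, and Appendix 3 says that JAK inhibitors and S1P modulators carry a significantly increased risk. If such cells run short, the unvaccinated HZ rate is too low as a reference for the vaccinated rate printed beside it. The exposure is greatest in exploratory objectives 3-4, where the side-by-side figures are the only comparison offered. A standardized difference computed without weights would also show imbalance on a variable that was matched exactly.

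**Working it through.** The protocol states no set-size distribution and no weighted or crude rate, so there is no plan figure to reproduce for this point. Table 6 was checked as background. With "a ratio of RZV vaccinated to RZV unvaccinated of 1:3" held fixed, 3.5 years, and 7% and 25% read as annual loss hazards, all 16 rows come back within 0.6% (at 15 per 1000: 880, 1160, 1584 and 2248 against the stated 876, 1164, 1588 and 2256). Nothing below changes it.

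**Step 1. Share of IBD vaccinees aged 70+.** Inputs: Table 5 and its footnote 3 (0.55% of vaccinees aged 50+ have IBD), and Table 2.
- Two-dose recipients aged 50+: 96 + 386 + 58 + 220 + (40,000 × 0.0055 = 220) + (27,000 × 0.0055 = 148.5) = 1,128.5.
- Fraction aged 70+ among vaccinees aged 50+: 333/(401 + 333) = 0.454, giving about 512 people.
- Share of the 1,385 projected: 512/1,385 = 37%. The 43.6% in Table 2 describes first-dose recipients through 12/2019, before the indication was widened.

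**Step 2. Supply of comparators at age level.**
- IBD 70+: 1,742/512 = 3.4 per vaccinee, before splitting by UC/CD, sex, decade, medication category and possibly race/ethnicity.
- RA 70+: two-dose recipients aged 50+ are 118 + 505 + 112 + 364 + (40,000 × 0.0091 = 364) + (27,000 × 0.0091 = 245.7) = 1,708.7. Multiplied by 607/1,218 this is about 852, and 4,797/852 = 5.6 per vaccinee.

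So IBD sits just above three at age level, and RA well above. Any shortage would lie in joint cells, more likely in IBD.

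**Step 3. Effect on the rate.** With p the share of vaccinees in a cell, m the comparators per set and r the unvaccinated rate:
- rate on the vaccinated mix = Σ p·r
- pooled rate = Σ p·m·r / Σ p·m

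Assumptions not in the protocol: r = 20 per 1000 at 70+ and 12 below (the ends of the overall range in section 11.1.1), three comparators in all sets below 70, and equal follow-up across cells. The rate on the vaccinated mix is 0.37 × 20 + 0.63 × 12 = 14.96.

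| Comparators per 70+ set | Comparator share aged 70+ | Pooled rate | Shortfall |
|---|---|---|---|
| 3 | 0.37 | 14.96 | 0 |
| 2 | 0.74/(0.74 + 1.89) = 0.281 | 12 + 8 × 0.281 = 14.25 | 4.7% |
| 1 | 0.37/(0.37 + 1.89) = 0.164 | 12 + 8 × 0.164 = 13.31 | 11.0% |

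At two comparators the unweighted standardized difference for age 70+ is (0.37 − 0.281)/√[(0.37 × 0.63 + 0.281 × 0.719)/2] = 0.19, despite exact matching on decade.

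**Step 4. A sparse joint cell instead of an age band.** Suppose a share s of vaccinees is matched 1:1 and the rest 1:3, with a base rate of 15 and a sparse-cell rate 1.5 to 3 times that. The shortfall is 1.6-6.0% at s = 5% and 3.1-10.7% at s = 10%. For example, at s = 10% and twice the rate: (0.9 × 3 × 15 + 0.1 × 30)/(0.9 × 3 + 0.1) = 15.54, against 0.9 × 15 + 0.1 × 30 = 16.5, or 5.8% low.

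**Step 5. The hazard ratio.** One deliberately extreme simulation used 20,000 sets, 30% of them 1:1 at three times the base rate, and a true HR of 0.30. The pooled unvaccinated rate was 19.4 per 1000 and the weighted rate 24.7. Cox stratified on the matched set gave 0.293; unstratified Cox gave 0.370.

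**The case against.** The strongest reply is that this is a reporting matter with no primary consequence. VE comes only from the Cox HR and never from a ratio of rates. The rate is labelled as that of the matched unvaccinated cohort, not as one standardised to vaccinees. The protocol does not say that standardized differences will be unweighted; that detail belongs naturally in a SAP. The protocol also limits sparse cells, by merging medication categories and by matching on race/ethnicity only if numbers allow. All of this stands. What remains is that the rate formula is stated, the rate is a listed outcome of the primary objectives, and complications have no matched-set estimate to set beside the pooled figures.

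Three stronger readings are tempting and are not supported:
- **That VE is biased.** With a true VE of 70%, the rates in Step 3 would imply 1 − 0.3 × 14.96/14.25 = 68.5%, or 66.3% at one comparator. The study does not calculate that quantity.
- **That comparators are known to be short.** Table 2's unequal age shares do not show scarcity; counts do. Subtracting future vaccinees from the IBD 70+ pool would give about 1,222, or 2.4 per vaccinee. But section 7.4 keeps people eligible until they receive a dose, so the subtraction is not justified. A pool fixed at 1/1/2020 also ignores people ageing into the band and new diagnoses. RA shows no shortage at age level.
- **That false imbalance will drive covariate choice.** Sections 6.3.1 and 11.2.2 do not tie adjustment to standardized differences.

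**Conclusion.** The point holds as a minor one. The stated rate rule, combined with a variable matching ratio, may give an unvaccinated HZ rate that does not carry the vaccinated mix, and it would be too low if small sets fall in higher-risk cells. The shortfall is about 5% to 11% in IBD under the assumptions in Step 3 and zero if every set reaches three. The set-size averages and the age-specific rates are assumptions; the protocol supplies neither. The 37% share rests on projecting the early age split forward.

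The primary VE is not affected if the Cox strata are the matched sets; section 11.2.2 says stratified without naming the strata. Sample size is unchanged. The reach is limited to the descriptive HZ rates, the exploratory complication figures and, if they are computed without weights, the standardized differences.

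**What to change.** In sections 11.2.1 and 11.2.4, state that comparator HZ rates, complication rates and proportions, and standardized differences will be reported with each comparator weighted by 1/(number of comparators in its set), beside the raw counts. For rates, apply the weight to both cases and person-years. Use set-clustered confidence intervals, and report the distribution of set sizes for each matched cohort.

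Add that the weights restore the mix at the index date only. They do not correct the later shift in person-time from unequal censoring, which section 11.1.1 assumes to be 7% in the vaccinated and 25% in the unvaccinated, so weighted rates need not agree exactly with the HR.

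The cost is one derived variable, a sentence in each of the two sections, and slightly wider intervals for the comparator rate. If every set reaches three, the weighted and raw point estimates coincide and nothing is lost.
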